#### ◆ Incident HIV diagnosis among CAB LA PrEP users (Objective 3.6)

- HIV diagnosis during periods of CAB LA PrEP use

Describe:

- HIV testing (timing and detailed assay results)
- Adherence to injection schedule
- HIV treatment
- Viral load measurements timing and results and if viral suppression was obtained
- Concomitant STI diagnosis
- HIV drug resistance

- HIV diagnosis after CAB LA PrEP discontinuation

Describe:

- HIV testing (timing and detailed assay results)
- Days between the last CAB LA injection and HIV diagnosis

#### 7.3.4. Confounders and effect modifiers

Not applicable; this study is descriptive in nature.

#### 7.4. Data sources

The Veterans Health Administration (VHA) is the largest integrated health care system in the United States, providing care at 1,380 health care facilities, including 170 VA Medical Centers and 1,193 outpatient sites of care of varying complexity (VHA outpatient clinics) to over 9.1 million Veterans enrolled in the VA health care program (US Department of Veterans Affairs, 2025).

In this study, we used data extracted from VHA's Corporate Data Warehouse (CDW), a comprehensive, continually updated repository of information from VHA's electronic health records (EHR) and administrative files. The CDW dataset includes health care encounters, laboratory tests and results, medications, diagnoses, patient demographics, and residential ZIP codes. The VACS-National Sample represents all ~13.5 million patients who have accessed VA care since 2000, with ~6 million patients accessing care annually (Yale School of Medicine, 2024).

## 7.5. Study size

This study is not designed for hypothesis testing but aims to evaluate usage patterns of oral PrEP and CAB LA PrEP in clinical practice. Additionally, it seeks to describe the incidence of HIV diagnoses among Veterans in care, including their PrEP history, as well as the incidence of HIV and other STI diagnoses among Veterans not on PrEP but potentially eligible for it. The study focuses on multiple outcomes of interest, with several parameters to be estimated.

For the objective related to HIV incidence among Veterans, the study will leverage data from the entire eligible population of Veterans in care.

Regarding PrEP usage patterns, a feasibility assessment identified 15,477 oral PrEP users and 748 CAB LA PrEP users between January 1, 2021 and June 30, 2025.

Table 4 provides precision estimates for proportions using a 95% confidence level, calculated using the standard confidence intervals equation  $[p \pm 1.96\sqrt{(p*(1-p)/N)}]$ . In the oral PrEP group, confidence interval widths for evaluated proportions range from 0.01 to 0.02. For the CAB LA PrEP group, the confidence interval width ranges from 0.04 to 0.07.

For instance, if the proportion of individuals having a complete CAB LA PrEP initiation is 80%, the 95% confidence interval around this estimate will be 77-83%.

**Table 4:** Precision estimates based on sample size and event proportions, using a 95% confidence level

PrEP formulation	Sample Size	Event Proportion	Lower Limit	Upper Limit	CI Width
CAB LA	748	0.1	0.08	0.12	0.04
	748	0.2	0.17	0.23	0.06
	748	0.3	0.27	0.33	0.07
	748	0.4	0.36	0.43	0.07
	748	0.5	0.46	0.54	0.07
	748	0.6	0.57	0.64	0.07
	748	0.7	0.67	0.73	0.07
	748	0.8	0.77	0.83	0.06
	748	0.9	0.88	0.92	0.04
Oral PrEP	15477	0.1	0.10	0.10	0.01
	15477	0.2	0.19	0.21	0.01
	15477	0.3	0.29	0.31	0.01
	15477	0.4	0.39	0.41	0.02
	15477	0.5	0.49	0.51	0.02
	15477	0.6	0.59	0.61	0.02
	15477	0.7	0.69	0.71	0.01
	15477	0.8	0.79	0.81	0.01
	15477	0.9	0.90	0.90	0.01

## 7.6. Data management

Study related data will be requested, accessed, maintained, cleaned and analyzed from the central data repository in a study specific DataMart on the VA Informatics and Computing Infrastructure (VINCI) and a local VA server (vhaconapp17.v01.med.va.gov). Data will be accessible only to a limited number of trained and certified VA employees. All researchers approved to utilize the resource will be required to maintain all relevant VA trainings and credentialing for research and agree to sign the rules of behavior for use of the data and computing environment.

## 7.7. Data analysis

All analyses conducted for this study will be descriptive and will aim at estimating frequencies of outcomes.

### 7.7.1. Primary analysis

#### 7.7.1.1. Main Analytical approach

##### **Veterans in care without HIV (Objective 1.1)**

For each calendar year during the study period, the number and percentage of new HIV diagnoses will be reported out of all individuals receiving care in the VHA healthcare system.

##### **Veterans in care with a new HIV diagnosis (Objective 1.2)**

Among newly diagnosed people with HIV, PrEP use (never, use within  $\leq 12$  months before diagnosis, use  $> 12$  months before diagnosis) and PrEP users' characteristics will be described using counts and proportions for categorical variables and median and interquartile ranges for continuous variables.

##### **Veterans who are not on PrEP and who could benefit from PrEP (Objective set 2)**

Baseline demographic and clinical characteristics will be described at the first visit during the study period meeting one of the criteria (index date), using median and interquartile ranges for continuous variables and counts and proportions for categorical variables. The frequency and rate (per 100 person-years) of HIV testing, HIV diagnoses, STI testing/screening, and STI diagnoses will be described within 12-months of the index date.

Rates of HIV tests and diagnoses as well as STI tests and diagnoses over this 12-month period will be estimated using univariate Poisson regression

##### **Veterans using PrEP (Objective set 3)**

**Objective 3.1-** Baseline demographic and clinical characteristics will be described at the start of PrEP use during the study period, by regimen type (oral or CAB LA), using median and interquartile ranges for continuous variables and counts and proportions for categorical variables.

**Objective 3.2-** The proportions of Veterans on care initiating CAB LA PrEP who used oral lead in (OLI) and proportion of those with direct to injection (DTI) will be calculated.

**Objective 3.3 and 3.4-** PrEP adherence and usage patterns will be described using median and interquartile range for continuous data as well as absolute and relative frequencies for categorical data. The percentage of days with access to oral PrEP and CAB LA PrEP will be described over the first 12 months after index PrEP initiation. Characteristics of individuals with and without delayed CAB LA injections as well as individuals with and without discontinuation will be compared using Pearson's chi-square tests for categorical variables and Mann-Whitney tests for continuous variables.

**Objective 3.5-** Incidence rates and confidence intervals for HIV testing, HIV diagnosis, STI testing/screening and STI diagnosis will be calculated using univariate Poisson regression. STI treatment prescription will be described using absolute and relative frequencies for categorical data.

**Objective 3.6-** For CAB LA PrEP users diagnosed with HIV, a timeline including details of oral PrEP prescriptions prior to CAB LA PrEP start, injections received, HIV tests performed, HIV treatment, viral load measurements, HIV drug resistance will be provided for each individual.

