**Objective set 2- Veterans in care with no evidence of HIV infection who are not on PrEP but could benefit from PrEP**

- 2.1- Describe the characteristics of Veterans in care who are not on PrEP but could benefit from PrEP
- 2.2- Estimate HIV testing and diagnoses rates, as well as rates of STI screening/testing rates, STI diagnoses among Veterans in care who are not on PrEP but could benefit from PrEP, over a 12-month period of follow-up

**Objective set 3- Veterans on care with no evidence of HIV infection who initiate PrEP (oral or CAB LA injectable) during the study period**

- 3.1- Describe the population of Veterans in care who initiated oral PrEP or CAB LA injectable PrEP, including their demographic, clinical and sexual behavioral characteristics, the year of PrEP initiation and the duration of follow-up
- 3.2- Describe the proportions of Veterans on care initiating CAB LA PrEP who used oral lead in (OLI) and proportion of those with direct to injection (DTI).
- 3.3- Describe adherence to oral and CAB LA injectable PrEP
- a) Oral PrEP use only: number days oral PrEP supplied divided by number of days in observational period
  - b) CAB LA injectable PrEP
    - Number of days covered by CAB LA PrEP divided by the number of days in the observation period
    - Timing and completion of initiation injections
    - Among complete initiators with at least one maintenance injection, timing of maintenance injections: all on time, any late injection (short delay not requiring reinitiation, long delay requiring reinitiation)
    - Baseline characteristics of users with all injections on time versus users with any late maintenance injection
- 3.4- Describe patterns of PrEP use
- a) Oral PrEP:
    - Discontinuation: any discontinuation, resumption of oral PrEP
    - Duration of oral PrEP use for the first period of use
  - b) CAB LA injectable PrEP
    - Discontinuation: any discontinuation, resumption of long-acting injections (with CAB LA injectable or LEN LA injectable) or oral PrEP after discontinuation
    - Oral bridging between discontinuation of CAB LA injections and resumption of CAB LA injections
    - Duration of CAB LA PrEP use in months

- first period of use
  - cumulative use throughout the study period in case of discontinuation followed by resumption of CAB LA PrEP injection(s)
  - Baseline characteristics of users discontinuing CAB LA PrEP versus users who did not discontinue

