## **7. RESEARCH METHODS**

### **7.1. Study Design**

This is a cohort study using data from the Veterans Affairs National Sample, which is composed of Veterans who receive healthcare services through the Veterans Health Administration (VHA). This national sample is representative of the Veteran population, capturing a wide range of demographic, clinical, and social characteristics.

Data will be extracted from VHA's Corporate Data Warehouse (CDW), a comprehensive, regularly updated repository of information from VHA's electronic health records and administrative files. It includes patient-level data such as demographics, clinical encounters (diagnoses, interventions), laboratory and imaging results, medication details, health services utilization, and long-term health outcomes.

The study period will range from January 1, 2021, to December 31, 2025. Initiation of PrEP regimen will be assessed during the period January 1, 2021 to June 30, 2025, to allow for at least 6 months of observation following PrEP initiation.

The study will include different cohorts, as described in Table 2.

Veterans who are not on PrEP but could benefit from PrEP will be identified based on risk factors for HIV acquisition or factors linked to behaviors increasing the risk of HIV acquisition which are generally documented in Veterans health records. These risk factors include: tested for or diagnosed with a bacterial STI in the past 12 months (gonorrhea, syphilis, chlamydia) (US CDC, 2024), tested for HIV in the past 12 months, ever had alcohol use disorder (Williams, 2016), ever used illicit non-injection drugs (HIV.gov, 2024), ever used injectable drugs (CDC, 2024), Black women (CDC, 2024; Reaves, 2025), men who have sex with men (CDC, 2022; Mayer, 2021), individuals aged 18-24 years (HIV.gov, 2025 b), any history of PrEP use (Hojilla, 2021; Krakower, 2019).

---

 The US CDC recommends PrEP for people with a bacterial STI diagnosis in the past 6 months. This has been extended to testing for a bacterial STI in the past 12 months for this protocol.

**Table 2:** Description of study cohorts

Objectives	Criteria	
Objective 1a - Among all Veterans without evidence of HIV infection	Population/exposure	No evidence of HIV diagnosis at beginning of each calendar year of the study period under analysis
	Index date	N/A
	Censoring criteria	N/A
	Endpoint	HIV diagnosis

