## 7.2. Study Population and Setting

### 7.2.1. Inclusion criteria

- **Veterans in care without evidence of HIV infection (Obj. 1.1)- individuals will be included if they meet all of the following criteria:**

- At least one VHA health encounter in the calendar year
- $\geq 18$  years of age
- No evidence of HIV infection at the beginning of the calendar year under analysis

- **Veterans in care with a new HIV diagnosis (Obj. 1.2):**

- Incident HIV diagnosis (refer to definition in section 7.3.3)

- **Veterans in care without evidence of HIV infection who are not on PrEP but who could benefit from PrEP (Objective set 2)- individuals meeting all of the following criteria:**

- At least one VHA health encounter during the study period
- $\geq 18$  years of age
- Any of the following criteria indicating that the individual has a risk factor for HIV acquisition or a factor linked to behaviors increasing the risk of HIV acquisition and may benefit from PrEP:
  - tested for or diagnosed with a bacterial STI in the past 12 months (gonorrhea, syphilis, chlamydia),
  - tested for HIV in the past 12 months,
  - ever had alcohol use disorder,
  - ever used illicit non-injection drugs,
  - ever used injectable drugs,
  - Black women,
  - men who have sex with men,
  - individuals aged 18-24 years,
  - any history of PrEP use
- No evidence of HIV infection at the first health encounter with a criteria for PrEP

- **Veterans in care using oral PrEP only (objective set 3)**

- At least one VHA health encounter during the study period
- $\geq 18$  years of age
- Received at least one oral PrEP prescription (TDF/FTC, TAF/FTC) between January 1 2021 and 31 December 2024
- No evidence of HIV infection at the time of the first oral PrEP prescription in the study period
- Have not received a CAB LA PrEP injection between January 1, 2021, and June 30, 2025

- **Veterans in care using CAB LA for PrEP (objective set 3)**

- At least one VHA health encounter during the study period
- $\geq 18$  years of age
- Received at least one CAB LA PrEP injection between January 1, 2021 and June 30, 2025

- No evidence of HIV infection at the time of the first CAB LA PrEP injection in the study period

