**Table 3:** Timing of CAB LA PrEP maintenance injections, among complete initiators with  $\geq$  maintenance injection

Dosing pattern	Timing of maintenance injections (following previous injection)
On-time	53-67 days
Late	68-127 days
Short delay not requiring reinitiation	68-97 days
Long delay requiring reinitiation	98-127 days
Discontinuation	>127 days without injection

◆ **Patterns of PrEP use (Objective 3.4)**

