**b) CAB LA PrEP: among complete initiators with at least one maintenance injection**

- Total number maintenance injections administered during first period of CAB LA PrEP use (overall and by person)

- Total follow-up time for complete CAB LA initiators with at least one maintenance injection (from first CAB LA PrEP injection to study end, loss to follow-up, death or HIV acquisition, whatever comes first)
- Discontinuation: number of individuals discontinuing CAB LA PrEP and number of individuals resuming LA PrEP injections (additional CAB LA or LEN LA injections after discontinuation and time between the last injection prior discontinuation and the first injection post-discontinuation) or oral PrEP
- Oral bridging between discontinuation of CAB LA injections and resumption of CAB LA injections
- Months on regimen until first censoring (first period of CAB LA PrEP use)  
Calculated as: days from first initiation injection to censoring (study end, loss to follow-up, death, HIV acquisition, discontinuation)
- Cumulative months on regimen across all CAB LA PrEP use (including additional injections after discontinuation)
  - Continuous time on CAB LA PrEP will be calculated as:
    - If no discontinuation: days from first initiation injection to censoring (study end, loss to follow-up, death, HIV acquisition)
    - If discontinuation: days from first initiation injection to discontinuation date (i.e., 127 days after last injection)
  - Among individuals with additional injections after discontinuation, the cumulative months on CAB LA regimen will be calculated across all episodes of continuous CAB LA PrEP use
  - Individuals with incomplete initiation of their first period of CAB LA PrEP use will be excluded from this analysis even if they have additional injections after incomplete initiation
- On CAB LA PrEP at timepoints of interest – among CAB LA users with no discontinuation and among CAB LA users with discontinuation
  - 12 months: injection received between  $\geq 238$  to  $\leq 365$  days after index (up to 127 days before the 12-month mark)
  - 24 months: injection received between  $\geq 603$  to  $\leq 730$  days after index (up to 127 days before the 24-month mark)
  - Study end: injection received up to 127 days before or on study end date
- ◆ **HIV testing & STI testing/screening during first period of PrEP use (Objectives 3.5)**
  - HIV testing

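### The baseline comparison of CAB LA users with and without discontinuation ignores unequal follow-up (184 days to about 4 years), so it is partly confounded by start date

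*Protocol*

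**What the plan says.** Section 6, Objective 3.4 b), asks for this contrast: "Baseline characteristics of users discontinuing CAB LA PrEP versus users who did not discontinue". Section 7.7.1.1 fixes the method: "individuals with and without discontinuation will be compared using Pearson's chi-square tests for categorical variables and Mann-Whitney tests for continuous variables". The synopsis repeats it.

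The other elements are fixed elsewhere in the protocol:

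- **Population.** Section 7.3.3, Objective 3.4, restricts the patterns of use: "CAB LA PrEP: among complete initiators with at least one maintenance injection".
- **Event.** Table 3 defines discontinuation as ">127 days without injection". Section 7.3.3 dates it by "days from first initiation injection to discontinuation date (i.e., 127 days after last injection").
- **Entry window.** Section 7.2.1: "Received at least one CAB LA PrEP injection between January 1, 2021 and June 30, 2025".
- **End of data.** Section 7.1: "The study period will range from January 1, 2021, to December 31, 2025". The entry window closes earlier "to allow for at least 6 months of observation following PrEP initiation".

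No passage gives the baseline comparison a common follow-up window, a minimum period of opportunity or censoring. Section 7.3.4 sets confounders aside as not applicable.

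**The concern.** Whether a user counts as discontinued depends on two things: whether the user stops, and how long the user is watched. Here the second varies about eight-fold and is set by start date. Early starters have years in which a gap of more than 127 days can be recorded. Late starters have months, and the very last have no time in which the rule can be met. Late starters therefore collect in the group without discontinuation.

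A baseline characteristic that becomes more common among newer starters will then look less common among discontinuers, even if it has nothing to do with stopping. These are the only planned results on which users stop CAB LA. They come with significance tests and go to providers, decision-makers and authorities (Section 11).

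**Working it through.** **The plan's own timing figures.** The bounds for being on CAB LA at 12 and 24 months reproduce: 365 − 127 = 238 and 730 − 127 = 603. The promise of at least 6 months also holds: 30 June to 31 December 2025 is 184 days.

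**Spread of follow-up.** Section 5 dates FDA approval to December 2021. A start on 1 January 2022 gives 1,460 days to study end, and 1,460 / 184 = 7.9.

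**Earliest day on which discontinuation can be recorded.** The formula is day of second injection + interval to first maintenance injection + 128. On-time limits are 23-37 days (7.3.3) and 53-67 days (Table 3). The latest intervals allowed are 67 and 127 days.

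| Schedule | Day needed | Last start that can qualify | Days of entry window excluded |
|---|---|---|---|
| Fastest on time | 23 + 53 + 128 = 204 | 10 June 2025 | 20 |
| About days 30 and 90 | 30 + 60 + 128 = 218 | 27 May 2025 | 34 |
| Slowest on time | 37 + 67 + 128 = 232 | 13 May 2025 | 48 |
| Latest allowed | 67 + 127 + 128 = 322 | 12 February 2025 | 138 |

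All four exceed 184. For on-time users, 20 to 48 days is about 3 to 7 weeks of starts. In addition, anyone last injected on or after 26 August 2025 has at most 127 days to study end, so that last gap cannot count as discontinuation.

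**Unequal opportunity for the rest.** The protocol gives neither the start-date distribution nor the stopping rate, so both are assumed: starts uniform or linearly rising from January or July 2022, and constant stopping of 20%, 35% or 50% per year, identical for everyone.

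- Share classed as discontinued: 2-7% with 184-274 days of follow-up, against 45-87% with three years or more.
- Median follow-up: 677-1,058 days in discontinuers, against 384-701 days in the others.
- Probability that a discontinuer has the longer follow-up: 0.71-0.80.

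**Effect on the planned test.** Assumptions: 500 eligible users, median time to stopping 18-36 months, uniform or rising uptake from 2022, stopping unrelated to the characteristic, two-sided 5% level (the protocol states none). The drift is from the first to the last starters.

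| Drift in prevalence | Spurious gap | Chi-square rejection |
|---|---|---|
| None | none | about 5% |
| 30% to 40% | about 2-3 points | 6-11% |
| 30% to 50% | about 4-5 points | 11-23% |

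A separate set of runs with 600 users and the 20-50% yearly stopping rates gave 3.6-6.0 points and 10-30% rejection for the 30%-to-50% drift.

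**Check of the remedy.** Classifying discontinuation by day 365 among users with at least 365 days of follow-up brought rejection back to about 4-6% under the same drift.

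**The case against.** **The study is descriptive.** Sections 7.5 and 7.7 say that it is not built for hypothesis testing, and Objective 3.4 asks for the characteristics of two observed groups, not for predictors of stopping. This limits the consequence. It does not remove the distortion, because the protocol itself plans significance tests on the split.

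**The protocol handles follow-up elsewhere.** Section 7.3.3 censors time on regimen and reports status at 12 and 24 months. Objective 3.1 reports year of initiation and duration of follow-up. A reader will have these beside the comparison, but none of them enters it.

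**The size is assumed.** The protocol offers no evidence that any characteristic drifts over start date. This stands: the figures are illustrations over a range, not forecasts.

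**Stronger readings that a reader might infer.**

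- *Recent starters in general cannot meet the 127-day rule.* Not so. The 184-day buffer is longer than 127 days, and strict impossibility arises only because a maintenance injection must come first. At the 218-day schedule it covers the last 34 days of starts, about 3% of users under uniform uptake from January 2022 and about 5% under rising uptake. Removing those users under a 30%-to-60% drift lowered rejection only from 18-41% to 15-36%. Most of the distortion is ordinary unequal follow-up.
- *The table contrasts early with late starters in place of stoppers with persisters.* Also not supported. Those recorded as discontinued did stop under the protocol's definition, and a probability of 0.71-0.80 shows partial mixing, not replacement.
- *Discontinuers are set against every other CAB LA user.* Section 7.3.3 limits the analysis to complete initiators with at least one maintenance injection.

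**Conclusion.** The point holds as partial confounding by start date. The comparison fixed in 7.7.1.1 takes no account of an eight-fold spread in follow-up. Non-discontinuation is automatic for on-time starters in about the last 3 to 7 weeks of the window and over-represented among other late starters. The date arithmetic rests on the protocol alone.

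The size rests on the assumed drift, uptake, stopping rate, number of eligible users and test level: modest at a 10-point drift, material at 20 points, absent with none. The direction does not depend on those values once a characteristic drifts. The comparison should be changed before the analysis. Results tables are planned for Q2 2027, so there is time.

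**What to change.** In 7.7.1.1, and in the matching synopsis text, replace the ever/never split with one of the following.

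1. **Fixed horizon (sufficient).** Compare users discontinued by 12 months with those not discontinued by then, among eligible users indexed by 31 December 2024. All have 365 days to study end, and even the latest allowed schedule (day 322) can meet the rule within that time. State how death, loss to follow-up or HIV acquisition before day 365 is classified. The chi-square and Mann-Whitney tests can stay. Cost: later discontinuations are not used, and some starters are lost. Under uniform uptake from January 2022, 1,095 / 1,276 = 86% are kept. Under linearly rising uptake from July 2022, (914 / 1,095)² = 70% are kept.

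2. **Time to discontinuation.** Describe it by baseline characteristic, censoring at study end, loss to follow-up, death or HIV acquisition. Start time at the first maintenance injection, or use delayed entry there. That injection is an entry condition, so timing from the first injection would count guaranteed event-free time. Stratification by start year is optional. Cost: all eligible users are kept, but a two-column table gives way to curves or hazard ratios.

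Both use data already planned for extraction and need only a change of wording and standard code.

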#### ◆ People without HIV who are not on PrEP and could benefit from PrEP (Objective set 2)

##### ◆ HIV testing & STI screening (Objective 2.2)

- HIV testing
  - Frequency and rate of HIV tests over 12-month period following the index date

- Type of HIV tests
- HIV diagnoses
  - Frequency and rate of new HIV diagnosis within 12 months of index date (first visit with at least one criteria for PrEP)  
Follow-up (FU) will be censored at first of:
    - HIV diagnosis
    - 12 months after index date
    - End of the study period
    - Loss to follow-up
    - Death
- STI testing/screening
  - Frequency and rate of STI testing events, overall (testing for multiple STIs on the same day will count as 1 testing event) and by type of STI tested  
Type of STI:
    - Syphilis
    - Gonorrhea
    - Chlamydia
    - Chancroid
    - Lymphogranuloma venereum
    - *Mycoplasma genitalium*
    - Hepatitis B virus (HBV)
    - Hepatitis C virus (HCV)
    - Genital Herpes (HSV-1, HSV-2)
    - Trichomoniasis
    - Genital Human papilloma virus (HPV) including warts  
Follow-up (FU) will be censored at first of:
    - HIV diagnosis
    - 12 months after index date
    - End of the study period
    - Loss to follow-up
    - Death
- STI diagnoses
  - Frequency and rate of new diagnosis of STI as noted in medical record or positive test result
  - STI diagnoses for
    - Syphilis
    - Gonorrhea
    - Chlamydia
    - Chancroid
    - Lymphogranuloma venereum
    - *Mycoplasma genitalium*
    - Hepatitis B virus (HBV)
    - Hepatitis C virus (HCV)
    - Genital Herpes (HSV-1, HSV-2)
    - Trichomoniasis

- Genital Human papilloma virus (HPV) including warts

◆ **PrEP users (Objective set 3)**

◆ **Use of oral lead-in (Objective 3.2)**

CAB PrEP formulation at initiation: proportion with CAB oral lead-in (OLI) vs. direct to injection (DTI)

◆ **Adherence (Objective 3.3)**

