    - Incidence proportion and incidence rate of HIV testing between the start of PrEP and the first discontinuation
    - Timing of HIV tests:
      - Oral PrEP: on-schedule testing defined as receiving an HIV test  $\leq 7$  days before/at start, and 3 months (76-104 days) after each test
      - CAB LA PrEP: on-schedule testing defined as receiving an HIV test

≤7 days before/at first injection, and 14 days prior each subsequent injection

- HIV diagnosis: incidence proportion and incidence rates between index date and the 1st discontinuation
- STI testing/screening
  - Assessed during the first period of PrEP use (oral or injectable)
    - Incidence proportion and incidence rate for STI testing/screening for
      - Gonorrhea
      - Chlamydia
      - Syphilis
      - Chancroid
      - Lymphogranuloma venereum
      - *Mycoplasma genitalium*
      - Hepatitis B virus (HBV)
      - Hepatitis C virus (HCV)
      - Genital Herpes (HSV-1, HSV-2)
      - Trichomoniasis
      - Genital Human papilloma virus (HPV) including warts
    - Interval between the first 2 tests for gonorrhea, chlamydia, syphilis done during the first period of PrEP use
      - Testing 3 months (76-104 days) after last test
      - Testing 6 months (168-196 days) after last test
      - Testing 12 months (351-379 days) after last test
- STI diagnoses
  - New diagnosis of STI as noted in medical record or positive test result
  - STI diagnoses for
    - Syphilis
    - Gonorrhea
    - Chlamydia
    - Chancroid
    - Lymphogranuloma venereum
    - *Mycoplasma genitalium*
    - Hepatitis B virus (HBV)
    - Hepatitis C virus (HCV)
    - Genital Herpes (HSV-1, HSV-2)
    - Trichomoniasis
    - Genital Human papilloma virus (HPV) including warts
- Relevant prescription for a selected list of STIs  
 Proportion of STI diagnosis with a prescription within 14 days following diagnosis as follows:
  - Syphilis: benzathine penicillin G, aqueous crystalline penicillin G, procaine penicillin G + probenecid, doxycycline
  - Gonorrhea: ceftriaxone, ceftriaxone + doxycycline, gentamicin + azithromycin,

- cefixime, cefotaxime
- Chlamydia: doxycycline, azithromycin, levofloxacin, amoxicillin
- Chancroid: azithromycin, ceftriaxone, ciprofloxacin, erythromycin base
- Lymphogranuloma venereum: doxycycline, azithromycin, erythromycin base
- *Mycoplasma genitalium*: doxycycline + azithromycin, doxycycline + moxifloxacin
- Trichomoniasis: metronidazole, tinidazole

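### Objective 3.5 takes every confidence interval from one Poisson regression; with ordinary errors it is miscalibrated for repeat tests and STIs, and undefined if no CAB LA user is diagnosed with HIV

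*Protocol*

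**What the plan says.** Section 7.7.1.1 of the protocol, Objective 3.5, reads: "Incidence rates and confidence intervals for HIV testing, HIV diagnosis, STI testing/screening and STI diagnosis will be calculated using univariate Poisson regression". The synopsis says the same. For Objective set 2, the same section reads: "Rates of HIV tests and diagnoses as well as STI tests and diagnoses over this 12-month period will be estimated using univariate Poisson regression". That sentence promises rates and does not mention intervals.

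The outcomes are defined in Section 7.3.3:

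- **Objective 2.2.** Events are counted, with the rule that "testing for multiple STIs on the same day will count as 1 testing event". One Veteran can therefore contribute several.
- **Objective 3.5, HIV testing.** The outcome is "Incidence proportion and incidence rate of HIV testing between the start of PrEP and the first discontinuation". On-schedule testing is a test about every three months on oral PrEP, and one before each injection on CAB LA. The text does not say whether the rate counts every test or only the first.
- **Objective 3.5, HIV diagnosis.** Both a proportion and a rate are wanted, from index date to first discontinuation.

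On size, Section 7.5 reports that "a feasibility assessment identified 15,477 oral PrEP users and 748 CAB LA PrEP users between January 1, 2021 and June 30, 2025". Its Table 4 gives precision for proportions only. The protocol gives no expected number of HIV diagnoses, no person-years and no dispersion.

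**The concern.** A Poisson model with its default errors assumes independent events and a variance equal to the mean. Tests and STI diagnoses are unlikely to satisfy this. Some Veterans have many more than others, which makes default intervals too narrow. HIV tests tied to a visit schedule may vary less than Poisson, which makes them too wide.

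HIV diagnosis raises a different problem. The CAB LA group is small, follow-up stops at first discontinuation, and the protocol describes PrEP as highly effective. If nobody is diagnosed, the estimated log rate is minus infinity and the regression returns no usable interval. A zero count is exactly the case in which readers need an upper limit.

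For Objective 3.5, these intervals are the only measure of sampling uncertainty that the protocol attaches to the rates.

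**Working it through.** **The plan's own precision figure.** Table 4 uses p ± 1.96·√(p(1−p)/N). With p = 0.8 and N = 748, 1.96·√(0.16/748) = 0.0287, so the limits are 0.771 and 0.829. The stated 77–83% is reproduced. No rate has a stated precision to reproduce.

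**Recurrent events.** Let φ be the variance-to-mean ratio of the per-person counts. The protocol does not give φ, so the values below are assumptions. A nominal 95% model-based interval covers 2Φ(1.96/√φ) − 1, and the correct interval is √φ times as wide. Overdispersed coverage was checked by negative binomial simulation with N = 748 and 5,000 runs.

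| φ | Coverage, formula | Coverage, simulated | Correct width ÷ model width |
|---|---|---|---|
| 0.5 | 99.4% | not run | 0.71 |
| 1.5 | 89% | 89–90% | 1.22 |
| 2 | 83% | 83% | 1.41 |
| 3 | 74% | 73–74% | 1.73 |

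For example, φ = 3 gives 1.96/1.732 = 1.132 and 2Φ(1.132) − 1 = 0.742.

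**HIV diagnosis on CAB LA.** Mean time in the first period of use is not given. I assume 0.5 to 2 years per user, so 374 to 1,496 person-years (PY), with 748 PY as the middle case. The true rate is also assumed. The chance of no event is exp(−rate × PY).

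| Assumed rate per 100 PY | 374 PY | 748 PY | 1,496 PY |
|---|---|---|---|
| 0.1 | 69% | 47% | 22% |
| 0.2 | 47% | 22% | 5% |
| 0.5 | 15% | 2% | 0.1% |

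At 748 PY and 0.1 per 100 PY, 0.748 events are expected and exp(−0.748) = 0.473. At 0.5 per 100 PY, 3.74 are expected and exp(−3.74) = 0.024.

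The Wald interval is (d/PY)·exp(±1.96/√d). The exact (Garwood) limits are χ²(0.025; 2d)/2 and χ²(0.975; 2d+2)/2, each divided by PY. At 748 PY, per 100 PY:

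| Diagnoses d | Wald | Exact |
|---|---|---|
| 0 | undefined | 0 to 0.49 |
| 1 | 0.019 to 0.949 | 0.003 to 0.745 |
| 3 | 0.129 to 1.244 | 0.083 to 1.172 |

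For d = 0 the exact upper limit is 3.69/748 = 0.0049 per PY. An intercept-only Poisson model fitted to 748 zeros failed, as expected. With no diagnoses, the exact upper limit is 0.99 per 100 PY at 374 PY and 0.25 at 1,496 PY.

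**The case against.** The strongest reply is that the protocol names a model but neither a variance estimator nor a type of limit, and that a SAP commonly fixes both. Robust errors are compatible with univariate Poisson regression. Section 7.8 also leaves methodological detail to the analyst and a methods catalogue. This stands as far as it goes: a reader might infer that the plan commits to default errors and that its intervals are wrong, and the text does not support that. It does, however, fix regression as the source of the intervals for both kinds of outcome. Followed with the usual errors, that leads to the results above.

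Four further points stand and limit the claim:

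- **Objective 2.2.** A reader might extend the interval criticism to it, but that text promises only rates.
- **All or first events.** Section 7.3.3 leaves this open for Objective 3.5. The repeated testing schedule, and the separate request for a proportion, suggest all events. If only first events are meant, the recurrence point falls away.
- **Direction and size.** Both depend on a dispersion that is not documented. With an assumed mean of 3 tests per person, the model-based half-width is 1.96/√(748·3) = 4.1% of the rate for CAB LA and 1.96/√(15,477·3) = 0.9% for oral PrEP. At φ = 2.5 (factor 1.58) these become 6.5% and 1.4%. The study is descriptive, and no test rests on these rates.
- **Zero events.** Only Wald limits fail. Exact and likelihood-based upper limits always exist. In the cases tabulated with one or three events, the Wald upper limit is above the exact one, so the upper bound is not understated there.

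**Conclusion.** The point holds in a limited form. With ordinary model-based errors and all events counted, the Objective 3.5 intervals for tests and STI diagnoses would be miscalibrated. They would cover about 89% to 74% if φ is 1.5 to 3, and more than 95% if schedule-driven testing makes φ less than 1. For HIV diagnosis on CAB LA, a count of zero is plausible: 47% to 2% at 748 PY for rates of 0.1 to 0.5 per 100 PY. In that case the Wald interval does not exist, although an exact interval of 0 to 0.49 per 100 PY would.

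The rates, person-years and dispersion are assumptions, not figures from the protocol. The documents do not support saying that the planned intervals are wrong in every case, or that no interval for CAB LA HIV incidence can be had. Severity is low and confidence moderate.

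**What to change.** In Section 7.7.1.1, with the synopsis brought into line:

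1. State that the Objective 3.5 rates count all events.
2. Keep the Poisson rate, but use robust (sandwich) standard errors clustered on Veteran for HIV testing, STI testing and STI diagnosis. This corrects errors in either direction.
3. Use exact (Garwood) Poisson limits for HIV diagnosis, and for any STI with few or no events, and say that they apply at zero events too.
4. Apply the same rules to Objective 2.2 if intervals are reported there.

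The cost is a sentence or two and a software option. Point estimates, cohorts and data extraction do not change. The downside is that some testing and STI intervals will be wider.
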